## 10.0 OUTCOME MEASURES

### 10.1 Primary Efficacy Endpoint

10.1.1 Time to first occurrence of death or cardiopulmonary hospitalization within each enrolling season

### 10.2 Secondary Efficacy Endpoints

10.2.1 Total (first and recurrent) cardiopulmonary hospitalizations or death

10.2.2 Time to first occurrence of cardiovascular death or cardiovascular hospitalization within each enrolling season

10.2.3 Time to first occurrence of death or cardiopulmonary hospitalization across all enrolling seasons

10.2.4 Time to first occurrence of the individual components of the primary endpoint

### 10.3 Exploratory Efficacy Endpoints

10.3.1 Time to first occurrence of all-cause death or cardiopulmonary hospitalization according to effectiveness of vaccine relative to virulence of influenza strain and the quality of the match between influenza strain and vaccine within individual seasons

10.3.2 Time to first occurrence of cardiovascular death or heart failure hospitalization

10.3.3 Time to first occurrence of cardiovascular death, non-fatal MI, or non-fatal stroke

10.3.4 Time to first occurrence of all-cause death or cardiopulmonary hospitalizations

### 10.4 Primary Safety Endpoint

10.4.1 Incidence of vaccine injection site reactions (described in section 11.0)

### 10.5 Secondary Safety Endpoints

10.5.1 Incidence of vaccine-related adverse events and serious adverse events

### 10.6 Correlative study endpoints

- 10.6.1 Immune Response Sub-Study (up to 3,000 subjects)**
- 10.6.1.1** Geometric mean titers post vaccination
  - 10.6.1.2** Change in antibody titers at 4 weeks post-vaccination from baseline
  - 10.6.1.3** Seroconversion, i.e. 4-fold rise in antibody concentrations from baseline to A/H1N1, A/H3N2, and B-type vaccine antigens
  - 10.6.1.4** Seroprotection, i.e. antibody titer levels  $\geq 1:40$  to the A/H1N1, A/H3N2, and B-type vaccine antigens 4 weeks following influenza vaccination. Seroconversion and seroprotection to A/H1N1, A/H1N3 strains and the B-Yamagata lineage.
- 10.6.2 ACHD Sub-Study**
- 10.6.2.1** Time to first occurrence of death or cardiopulmonary hospitalization within each influenza season in the ACHD population. (Appendix B)

## **11.0 ASSESSMENT OF SAFETY**

### **11.1 Specification of Safety Parameters**

#### **11.1.1 Definition of Adverse Events (AE)**

An AE is any untoward or unfavorable medical occurrence in a human subject, including any abnormal sign (for example, abnormal physical exam or laboratory finding), symptom, or disease, temporally associated with the subject's participation in the research, whether or not considered related to the subject's participation in the research.

#### **11.1.2 Definition of Serious Adverse Events (SAE)**

A SAE is one that meets one or more of the following criteria:

- Results in death
- Is life-threatening (places the subject at immediate risk of death from the event as it occurred)
- Results in inpatient hospitalization or prolongation of existing hospitalization
- Results in a persistent or significant disability or incapacity
- Results in a congenital anomaly or birth defect
- An important medical event that may not result in death, be life threatening, or require hospitalization may be considered an SAE when, based upon appropriate medical judgment, the event may jeopardize the subject and may require medical or surgical intervention to prevent one of the outcomes listed in this definition.

As death and hospitalizations for cardiovascular and pulmonary reasons are considered clinical endpoints for this trial, they will be reported in clinical study reports and publications as clinical endpoints.

#### **11.1.3 Definition of Unanticipated Problems (UP)**

An AE is considered unanticipated, when either the type of event or the severity of the event is not listed in the protocol or package insert/product monograph.

### **11.2 Classification of an Adverse Event**

#### **11.2.1 Severity of Event**

- Mild: no intervention required; no impact on activities of daily living (ADL)
- Moderate: minimal, local, or non-invasive intervention indicated; moderate impact on ADL
- Severe: significant symptoms requiring invasive intervention; subject seeks medical attention, needs major assistance with ADL

### 11.2.2 Relationship to Study Agent

- **Definitely Related** – There is clear evidence to suggest a causal relationship, and other possible contributing factors can be ruled out. The clinical event, including an abnormal laboratory test result, occurs in a plausible time relationship to drug administration and cannot be explained by concurrent disease or other drugs or chemicals.
- **Probably Related** – There is evidence to suggest a causal relationship, and the influence of other factors is unlikely. The clinical event, including an abnormal laboratory test result, occurs within a reasonable time after administration of the drug, is unlikely to be attributed to concurrent disease or other drugs or chemicals.
- **Possibly Related** – There is some evidence to suggest a causal relationship (e.g., the event occurred within a reasonable time after administration of the trial medication). However, other factors may have contributed to the event (e.g., the subject's clinical condition, other concomitant events). Although an AE may rate only as "possibly related" soon after discovery, it can be flagged as requiring more information and later be upgraded to "probably related" or "definitely related," as appropriate.
- **Unlikely to be related** – A clinical event, including an abnormal laboratory test result, whose temporal relationship to drug administration makes a causal relationship improbable (e.g., the event did not occur within a reasonable time after administration of the trial medication) and in which other drugs or chemicals or underlying disease provides plausible explanations (e.g., the subject's clinical condition, other concomitant treatments).
- **Not Related** – The AE is completely independent of study drug administration, and/or evidence exists that the event is definitely related to another etiology. There must be an alternative, definitive etiology documented by the clinician.

### 11.2.3 Follow-up of Subjects after a Reportable SAE

SAEs with a causal relationship to trial participation must be followed until the event or its sequelae resolve or stabilize to a level acceptable to the local investigator.

### 11.2.4 Expectedness

Expected events are those that have been previously identified as resulting from administration of the investigational product. An AE is considered unexpected, when either the type of event or the severity of the event is not listed in the protocol or package insert.

## 11.3 Time Period and Frequency for Event Assessment and Follow-Up

All adverse events temporally related (within 1 week) to vaccine administration will be collected on appropriate CRFs. Specific adverse events of interest (see section 11.4.4) will be queried.

All serious adverse events that are possible trial endpoints, including death and all hospitalizations, will be collected on appropriate endpoint collection forms. All other serious adverse events not covered by endpoint collection forms will be collected on appropriate SAE CRFs. CRFs will be completed at the time the event becomes known to study investigators, either by notification by the subject, or during influenza season surveillance, at which time

investigators will inquire about the occurrence of events since the last time of contact. Serious adverse events and trial endpoints (death or hospitalization) will be collected until July 31 of the influenza season.

All suspected unexpected serious adverse reactions (SUSARs) will be collected on appropriate CRFs during the course of the trial. All SUSARs will be collected at the time they are known to study investigators and may be subject to specific reporting requirements by health authorities or local IRBs.

Non-serious adverse events not temporally related to study vaccine administration (> 1 week) and not suspected to be related to study vaccine administration will be collected locally only, per GCP guidelines.

## **11.4 Reporting Procedures**

### **11.4.1 Adverse Event Reporting**

All adverse events that occur within 1 week of study vaccine administration will be collected and specific adverse events of interest (see section 11.4.4) will be queried. Non-serious adverse events not temporally related to study vaccine administration (> 1 week) and not suspected to be related to study vaccine administration will not be collected.

### **11.4.2 Serious Adverse Event Reporting**

All serious adverse events that are possible trial endpoints, including death and all hospitalizations, will be collected on appropriate endpoint collection forms. All other serious adverse events not covered by endpoint collection forms will be collected on appropriate SAE CRFs. CRFs will be completed at the time the event becomes known to study investigators, either by notification by the subject, or during influenza season surveillance, at which time investigators will inquire about the occurrence of events since the last time of contact. Serious adverse events and trial endpoints (death or hospitalization) will be collected until July 31 of the influenza season.

This trial has received an IND exemption, and serious adverse events will not be required to be reported to FDA. Serious, unexpected adverse drug reactions will be reported to Health Canada in an expedited manner as required (section 11.4.3). SAEs will be reported to local IRBs per local IRB requirements.

### **11.4.3 Unanticipated Problem Reporting**

All suspected unexpected serious adverse reactions (SUSARs) will be collected on appropriate CRFs during the course of the trial. All SUSARs will also be collected at the time they are known to study investigators. There is no requirement for SUSAR reporting to FDA because of the IND exemption, however, all fatal or life threatening SUSARs will be reported to Health Canada as soon as possible but no later than 7-15 calendar days after the event becomes known to study investigators. All non-fatal or non-life threatening SUSARs must be filed as soon as possible but no later than 15 calendar days after the event becomes known to study investigators. All SUSARs will be reported to Sanofi-Pasteur and to local IRBs as per local IRB requirements.

### **11.4.4 Adverse Events of Interest**

The following events occurring within one week of study vaccine administration are considered events of special interest and will be specifically queried:

- Injection site reactions (pain, redness, or swelling at injection site)
- Myalgia

- Fever
- Malaise
- Headache

The following important medical events will be considered SAEs and reported according to section 11.4.3:

- Guillain-Barré syndrome
- Bell's palsy
- Encephalitis/myelitis
- Optic neuritis
- Stevens-Johnson syndrome
- Toxic epidermal necrolysis

### **11.5 Study Termination Rules**

The DSMB may recommend stopping the study early if the incidence of safety events in the high-dose arm is unacceptably higher than in the standard-dose arm or for clear efficacy results. For additional details, see Section 13.14 on Stopping Rules for Termination of the Trial.

### **11.6 Unblinding Procedure**

Unblinding will be done in emergent circumstances where the identity of the study medication needs to be known. All efforts will be made to maintain blinding except in the case of urgent medical necessity. If a subject needs to be unblinded, the study staff should contact their assigned medical monitor within 24 hours. The study site must document who broke the blind and reason, and report the event to a member of the trial's executive leadership team ([name] or [name]) within 24 hours. Contact the medical monitor first, who will instruct the data coordinating center to unblind.

Unblinded subjects will not be re-vaccinated in subsequent influenza seasons as part of the trial and taken off study as of the date of the summer phone call contact following randomization or registration.

### **11.7 Safety Oversight**

Safety oversight will be under the direction of a DSMB composed of individuals with the appropriate expertise, including cardiovascular disease, pulmonary disease, infectious disease, statistics, and ethics. The DSMB will meet at least semiannually to assess safety and efficacy data on each arm of the study. The DSMB will operate under the rules of an approved charter that will be written and reviewed at the organizational meeting of the DSMB. At that time, each data element that the DSMB needs to assess will be clearly defined. The DSMB will provide its input to the NHLBI project office, and the study executive committee.

## **12.0 CORRELATIVE (IMMUNE RESPONSE, BIOMARKER AND DNA) STUDIES**

Antibody titers to influenza vaccine antigens, seroprotection, and seroconversion will be assessed in a subgroup of subjects (up to 3,000 subjects, approximately 1,000 subjects from each of the three influenza seasons) to test the hypothesis that a higher influenza vaccine dose will result in more pronounced humoral immune response, evidenced by greater mean titers post-vaccination and higher antibody titer changes from baseline, and to test the hypothesis that higher antibody concentrations will be associated with the reduced rate of the composite of all-cause death and cardiopulmonary hospitalization. Participation in correlative studies is optional.

Additional blood will be collected from a further subset of correlative study subjects for future research about biomarkers and DNA.

A subset of approximately 35 sites from geographically diverse regions in the US and Canada will be asked to participate in the humoral immune response sub-study.

### **12.1.1 Sample Collection Guidelines**

Subjects electing to participate in the optional correlative studies that become available after the Vanguard year will contribute two blood samples, one at baseline and a second sample two-four weeks after vaccination. At the first time point, 10 ml of blood will be collected in serum tubes for immune function analyses. At the second time point, 20 ml will be collected for immune function testing. At one of these timepoints, an additional 10 ml of blood will be collected in DNA collection tubes (only if the subject consents to banking of their blood for genetic testing).

Following the blood draw, the sampling tube should be stored at room temperature for a minimum of 60 minutes and a maximum of 2 hours to allow the blood to clot before centrifugation. The tube must be stored vertically and not shaken. Beyond 2 hours, the sampling tube must be refrigerated at a temperature of 2°C to 8°C and must be centrifuged within a maximum of 24 hours. After being allowed to clot for a minimum of 60 minutes to a maximum of 2 hours at room temperature (or after being refrigerated for 2 to 24 hours after collection), blood samples for serum antibody response assessment will be centrifuged before being divided into at least 3 aliquots, if possible. Sera will be placed in cryovials labeled with the study ID, collection number (#1 or #2), and collection season (i.e. 2016/17). Cryovials will be frozen at -20 degrees (or colder) and stored at the study sites. Once blood collection is completed or at the end of each influenza season, samples will be batch shipped to Brigham and Women's Hospital (U.S. sites) and Peter Munk Cardiac Centre (Canadian sites) for further analysis.

### **12.1.2 Assay Methodology for immune response studies**

Brigham and Women's Hospital and Peter Munk Cardiac Centre will ship two cryovials from each subject, labeled as described above, to Sanofi Pasteur, Inc. in Pennsylvania for analysis, accompanied by no other information. A hemagglutination inhibition assay (HIA) will be used to measure influenza antibody concentrations following immunization. HIA will be performed in duplicate using standard microtiter techniques. Briefly, influenza virus-induced agglutination of guinea pig red blood cells will be inhibited by antibodies present in the human serum. Serial dilutions of the human sera will be made. Titrated influenza antigen will be incubated with the serum dilutions for 30 minutes. Guinea pig red blood cells (50 µL of 0.5% in phosphate buffered saline) will be added and incubated for 45 minutes. The dilution of serum that no longer inhibits hemagglutinin signifies the influenza antibody titer. Sanofi Pasteur, Inc. will destroy the samples once analysis is complete.

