4.4. Correlative Study Endpoints for the Immune Response Substudy

- 4.4.1. Geometric mean titers post vaccination as well as at baseline
- 4.4.2. Change in antibody titers at 4 weeks post-vaccination from baseline
- 4.4.3. Seroconversion, i.e. 4-fold rise in antibody concentrations from baseline to A/H1N1, A/H3N2, and B-type vaccine antigens 4 weeks following influenza vaccination
- 4.4.4. Seroprotection, i.e. antibody titer levels $\geq 1:40$ to the A/H1N1, A/H3N2, and B-type vaccine antigens 4 weeks following influenza vaccination
- 4.4.5. Seroconversion, i.e. 4-fold rise in antibody concentrations from baseline to at least one vaccine antigen (A/H1N1, A/H3N2, or B-Victoria lineage for high dose and standard dose vaccines, and to B-Yamagata lineage for standard dose vaccine) 4 weeks following influenza vaccination
- 4.4.6. Seroprotection, i.e. antibody titer levels $\geq 1:40$ to at least one vaccine antigen (A/H1N1, A/H3N2, or B-Victoria lineage for high dose and standard dose vaccines,

and to B-Yamagata for standard dose vaccine) 4 weeks following influenza vaccination

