8.6 Analysis of the Correlative Endpoints for the Immune Response Substudy

Antibody titers at baseline and week 4, change in antibody titers from baseline to week 4, and the incidence of seroconversion and seroprotection in A/H1N1, A/H3N2 and B-type vaccine antigens and in A/H1N1, A/H3NW and B-Yamagata lineage at 4 weeks following vaccinations will be summarized with descriptive statistics such as geometric mean and standard deviation or median and IQR for quantitative measures and frequency and proportion for qualitative measures along with graphics such as box plots or empirical distribution functions and bar plots and compared between the two treatment arms using two-sample tests with robust variance to account for intra-subject correlation over multiple vaccinations.

Clinical outcomes will be compared between those with and those without overall seroconversion and seroprotection and antigen-specific seroconversion and seroprotection to A/H1N1, A/H3N2, B-Yamagata and B-Victoria vaccine antigens (for standard dose vaccine) and to A/H1N1, A/H3N2 and B-Victoria lineage (for high dose) using log-rank

tests. Cox proportional hazards regression analysis will be performed for the primary endpoint of the composite of all-cause death or cardiopulmonary hospitalization with the geometric mean titer across vaccine strains post-vaccination as a model term, instead of individual antibody titers, to avoid issues of collinearity, stratified by enrolling season, while adjusting for other covariates including treatment and other immune responses and the interaction between treatment and match for circulating B-Yamagata lineage that is included only in the standard-dose QIV (binary), based on influenza typing and subtyping data. The hazard ratio for each doubling of the geometric mean titer will be estimated along with confidence intervals from Cox proportional hazards regression analysis with robust variance estimation. Given that the traditional definition of seroprotection, namely HAI titers ≥ 40 , may be an inadequate estimate of a protective threshold during years of poor match between vaccine antigens and circulating strains, we will also assess seroprotection defined as HAI ≥ 80 , 160, and 320 as exploratory analyses.

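### Protocol 12.1.2 defines the HAI titer, read literally, as the first dilution that fails to inhibit, one step above the last inhibiting dilution, so the seroprotection cut-offs would act one step too low

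*Protocol*

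**What the plan says.** Protocol 12.1.2 describes the assay in a few sentences. It says that "HIA will be performed in duplicate using standard microtiter techniques", and that "influenza virus-induced agglutination of guinea pig red blood cells will be inhibited by antibodies present in the human serum". It continues: "Serial dilutions of the human sera will be made". It gives neither the dilution factor nor the starting dilution. The reading rule is then: "The dilution of serum that no longer inhibits hemagglutinin signifies the influenza antibody titer". No other section of the protocol or SAP defines the titer.

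The endpoints use the titer in two ways:

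- **Absolute cut-offs.** SAP 4.4.4 defines seroprotection as "antibody titer levels $\geq 1:40$ to the A/H1N1, A/H3N2, and B-type vaccine antigens 4 weeks following influenza vaccination". Protocol 10.6.1.4 uses the same cut-off, and SAP 4.4.6 applies it to at least one vaccine antigen. Protocol 13.7 and SAP 8.6 add exploratory cut-offs of 80, 160 and 320. SAP 8.6 also compares clinical outcomes between subjects with and without seroprotection, using log-rank tests.
- **Ratios.** Protocol 10.6.1.3 defines "Seroconversion, i.e. 4-fold rise in antibody concentrations from baseline to A/H1N1, A/H3N2, and B-type vaccine antigens". Protocol 13.7 and SAP 8.6 estimate a hazard ratio for each doubling of the geometric mean titer.

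**The concern.** By the protocol's own description, antibody shows itself by inhibiting agglutination. A dilution that has stopped inhibiting therefore shows no detected activity at that dilution, yet the written rule makes that dilution the titer. A cut-off of 1:40 should pick out sera still active at 1:40. Under the literal rule it also admits sera that stopped inhibiting exactly there.

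What is at stake is the scale of the absolute results: reported GMTs, seroprotection percentages at 40, and the exploratory question of whether 40 is too low a threshold. Misclassified subjects would also move from the non-seroprotected to the seroprotected group in the clinical-outcome comparison of SAP 8.6. As the text stands, a reader cannot tell which scale the results are on.

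**Working it through.** The plan states no figure that depends on this rule. The sub-study has a cap of up to 3,000 subjects and no power calculation, so there is nothing to reproduce first.

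**Inputs from the documents:** the reading rule (Protocol 12.1.2), the cut-offs 40, 80, 160 and 320 (SAP 4.4 and 8.6), the 4-fold rise (Protocol 10.6.1.3) and the doubling term (SAP 8.6).

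**Assumptions, because the documents are silent:** dilution factor *f*, starting dilution and titer distribution.

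**Step 1: the shift.** Let *L* be the last inhibiting dilution. The literal titer is *f* × *L*, so literal titer ≥ *c* is the same as *L* ≥ *c*/*f*.

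- Two-fold series from 1:5, 1:10 or 1:20: the sera wrongly passing 40 are those with *L* = 20. For 80, 160 and 320 they are those with *L* = 40, 80 and 160.
- Two-fold series from 1:8: 1:40 is not in the series, and the sera that cross go from 32 to 64.
- Four-fold series from 1:10: the shift is four times, for example 10 to 40.

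A serum that already fails at 1:20 in a two-fold series scores 20 or less under either rule and is not misclassified.

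**Step 2: size under a two-fold series.** Titers were simulated as normal on the log2 scale, with 400,000 draws per setting and a two-fold series from 1:10. A serum not inhibiting at 1:10 scored 5 under the highest-inhibiting rule and 10 under the literal rule.

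| Assumed GMT | SD (log2) | Seroprotected, highest inhibiting dilution | Seroprotected, literal rule | Overstatement (points) |
|---|---|---|---|---|
| 30 | 1.2 | 0.363 | 0.687 | 32.4 |
| 30 | 1.8 | 0.411 | 0.628 | 21.7 |
| 60 | 1.8 | 0.627 | 0.810 | 18.3 |
| 100 | 1.8 | 0.769 | 0.902 | 13.3 |
| 150 | 1.2 | 0.944 | 0.992 | 4.8 |

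The first and last rows are the extremes of the 12 settings run, giving roughly 5 to 32 points. Scored GMTs doubled, for example from 42.5 to 85.1 (assumed GMT 60, SD 1.2).

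**Step 3: what does not move.**

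- Fold rise: (*f* × post)/(*f* × baseline) = post/baseline. In the simulation the 4-fold rate was 0.459 under both rules (GMT 60, SD 1.2). The match was exact because the floor value 5 is half of 10; another floor rule could break it at the lower limit.
- Between-arm GMT ratio: *f* cancels.
- Hazard ratio per doubling: log2(*f* × *L*) = log2 *L* + log2 *f*. The added constant goes into the baseline hazard.
- Primary endpoint: it does not use titers.

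**Step 4: the between-arm seroprotection difference.** Use P(titer ≥ *c*) = 1 − Φ((log2 *c* − log2 GMT)/SD), with the literal rule replacing *c* by *c*/2. With equal SDs, the arm difference shrinks when the geometric midpoint of the two GMTs exceeds *c*/√2, and grows when it is lower. For *c* = 40 that point is 40/1.414 = 28.3; for *c* = 160 it is 113.

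- GMTs 60 and 100 (midpoint √6000 = 77.5), cut-off 40: the difference falls from 13.1 to 9.1 points (SD 2.0), or from 15.9 to 8.5 (SD 1.5).
- GMTs 15 and 25 (midpoint √375 = 19.4), cut-off 40: it grows from 12.8 to 14.6 points (SD 2.0), or from 15.3 to 19.4 (SD 1.5).
- GMTs 60 and 100, cut-off 160: it grows by the same amounts as the 15 and 25 pair at 40, because 160/60 = 40/15 and 160/100 = 40/25.

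The direction therefore depends on the titer level and the cut-off.

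**The case against.** The strongest reply is that this is one loose sentence in a short assay summary. The protocol points to standard microtiter technique, and the sentence itself names hemagglutinin where the assay measures inhibited agglutination. The sera go to one central laboratory and sites read nothing. The SAP, which governs the analysis, does not repeat the rule. The laboratory may well score the highest inhibiting dilution. This stands: the documents show a wrong or ambiguous written definition, and a reader who infers that the laboratory will mis-score goes further than they allow.

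Three other inferences are tempting and are not supported:

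- **Every titer is doubled.** That needs a two-fold series, which the documents do not state. A serum still inhibiting at the last dilution tested has no failing well to read.
- **Every serum that fails at 1:40 counts as seroprotected.** Only sera whose first failing dilution is 1:40 cross that cut-off.
- **The high-dose versus standard-dose difference in seroprotection shrinks.** It can also grow, and the documents give no titer distribution to settle which.

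It is also fair to say that the sub-study is optional. The samples reach the assay laboratory with only the study ID, collection number and season on the label, so any convention applies alike to both arms. The comparison of mean titers on the log scale survives a constant shift.

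What remains is that the only written definition, if followed, puts the absolute endpoints on the wrong scale, and nothing elsewhere corrects it.

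**Conclusion.** The point holds as a minor error in a written definition, confined to the absolute titer measures of the immune response sub-study: GMT levels, seroprotection at 40, the exploratory cut-offs, and the grouping by seroprotection in SAP 8.6.

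The one-step shift follows from the text alone. Its size does not. The doubling of GMTs assumes a two-fold series and excludes values at the assay limits. The 5 to 32 point overstatement also assumes log-normal titers with GMT 30 to 150 and SD 1.2 to 1.8 log2 units. The direction of any change in the between-arm seroprotection difference cannot be stated. Whether reported results are affected at all depends on the laboratory's actual convention, which the documents do not show.

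**What to change.** Replace the sentence in Protocol 12.1.2, or add a definition to SAP 4.4: the titer is the reciprocal of the highest serum dilution that completely inhibits hemagglutination, and a serum that does not inhibit at the first dilution is reported as below that dilution.

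Before analysis, ask the assay laboratory which convention its results file uses, the dilution factor, the starting dilution, and the values assigned below and above range. The same query can settle how duplicates are combined.

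Only if the written convention was used, divide titers by the dilution factor before applying the 40, 80, 160 and 320 cut-offs, and treat out-of-range values separately.

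The cost is one sentence and one query, with no new samples or assays. The downside is that reported GMTs and seroprotection rates may be lower.
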